Pretreatment plasma porphyrin levels in PCT are generally 10-25 mcg/dL (normal <0.9 mcg/dL). New skin lesions are unlikely after the plasma porphyrin concentration becomes normal. Friability, hypertrichosis, milia and areas of atrophy, scarring and hyper- or hypopigmentation improve over periods of weeks or months after this. Even scarring and the more extensive scarring and contraction (pseudoscleroderma) that sometimes occur in PCT can disappear (31), but showed little or no improvement in one series (39). Liver function abnormalities can also improve (40). Siderosis, needle-like inclusions, and red fluorescence in liver can be expected to improve or disappear, although other histological abnormalities may not (41, 42). After a remission is obtained, continued phlebotomies are usually not needed even if ferritin levels later increase to typical normal levels. However, it is advisable to follow porphyrin

levels and reinstitute treatment if porphyrin levels begin to rise. Relapses are reported to respond to another course of phlebotomies.

The time to remission with phlebotomy is not well established in the literature to serve as a standard to compare with other treatments, since many studies did not follow ferritin and plasma or urine porphyrin levels during treatment. Reports that phlebotomies for as long as one year are necessary for remission (43, 44) are not consistent with experience at most centers. Our experience and the interim analysis for this study indicate that with good adherence to scheduled phlebotomies the target ferritin can be reached in 3-4 months in most cases, and remission can be achieved in 6-7 months (19, 45).

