Figure 2. Enrollment, assignment to treatment with or without randomization of 48 study patients with PCT in the interim analysis, and inclusion of the 30 patients who achieved a normal plasma porphyrin concentration in the analysis comparing time to remission with phlebotomy and low-dose hydroxychloroquine.

porphyrin level may not be a sign of full remission. Therefore, continuing treatment with

hydroxychloroquine until these additional outcome measures become normal may be beneficial. There were no significant side effects with either treatment. Follow up was insufficient to compare recurrence rates with these treatments.

Based on these interim findings we concluded that (1) the study should continue with changes to better assess response and durability with these two standard treatments. (2) Time to achieving treatment endpoints in addition to normal plasma porphyrin levels should be assessed. (3) All available PCT patients who require treatment should be enrolled, if possible, and assigned treatment based on medical indications, preference, or randomization (for patients suitable for either treatment). (4) A noninferiority design is not appropriate, because most subjects are not randomized, and outcomes should be compared using descriptive methods. (5) Power analyses to assess effects of clinical features and susceptibility factors should emphasize those of greatest clinical interest. We consider that age and sex are the clinical features of greatest interest, and alcohol use, hepatitis C and UROD mutations are susceptibility factors of greatest interest. (6) Longer follow up is needed to assess durability of treatment, and whether this relates to susceptibility factors. (7) The single primary outcome was evaluable in ~2/3 of patients in the interim analysis. Inclusion of additional outcomes is likely to provide evaluable outcomes for a greater proportion of patients. (8) This study also will provide serial data and samples on a cohort of PCT participants in whom treatment responses and complete remission are rigorously documented, which will be valuable for future cross sectional and longitudinal research on the pathogenesis and natural history of this disease.

3. Specific aims

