- 5. Normal pattern of urine porphyrins by HPLC

How quickly each of these targets and outcomes will be achieved will vary greatly among patients. Therefore, levels need to be followed closely to anticipate when visits are needed to document treatment outcomes. If less frequent visits than recommended are contemplated, site investigators should review laboratory results within 3 days of receiving the reports and determine when the next visit and the next set of tests should be done in order to document all primary and secondary outcomes.

To be considered an evaluable outcome, time to achieving each of the study outcomes listed above (e.g. time to achieving a normal plasma porphyrin level) will be documented by an abnormal finding (e.g. a high plasma porphyrin level) followed by normalization of that finding

(e.g. achieving a normal plasma porphyrin level) within a specified time interval, which is referred to as the *documentation window* for achieving that outcome. That interval/documentation window will be 4 weeks for achieving a normal plasma porphyrin concentration, and 8 weeks for achieving the later biochemical outcomes. Therefore, a single missed visit that is not within one of these windows should not lead to a missed verification of a treatment outcome.

The following study practices are recommended to document the major study outcomes:

- 1. A phlebotomy patient should return every 2 weeks after the ferritin falls to 60 ng/mL, in order to either 1) document a ferritin of 25 ng/mL on the day of the last phlebotomy, or if serum ferritin was not measured on the day of the last phlebotomy, 2) to document a ferritin level of <20 ng/mL ~2 weeks after the last phlebotomy.
- 2. Once the plasma porphyrin level drops to less than ~4 mcg/dL, this test should be repeated biweekly to ensure that, even if a visit is missed, normalization is captured within the 4-week documentation window, which will properly document time to this primary treatment outcome.
- 3. After the plasma porphyrin concentration is normal (<0.9 mcg/dL), visits should be scheduled at 4 week intervals until the other outcomes are achieved. If visits are missed intermittently, this will still allow capturing a change from abnormal to normal within an 8-week documentation window.

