4.D. Recruitment and availability. Participants with PCT will be obtained primarily by referral to the participating centers. Physicians in primary care and specialty clinics such as dermatology and gastroenterology are made aware through personal contacts and notices of this treatment study and asked to refer participants. Notices are also sent to primary physicians and specialists in the referral area for each center in order to attract additional participants. We anticipate enrolling ~60 additional participants over the second 5-year cycle of funding of the Porphyrias Consortium to bring the total enrollment to at least 100. Thus the total target enrollment period will be 10 years.

Feasibility of recruitment is based on data from UTMB, which has been studying PCT and capturing all patients seen at that institution for many years. On average, we expect to enroll 8-10 patients with new onset or recurrent PCT per year at UTMB. Over the second 5-year period of Porphyrias Consortium funding we can expect to enroll a total of 40-50 patients at UTMB. With contribution from the other 6 centers, we expect to achieve the recruitment objective of ~60 new patients.

4.E. Enrollment and treatment assignment. Subjects will be enrolled if they meet the inclusion and exclusion criteria shown in Table 1, which should allow inclusion of the great majority of individuals who present with PCT. PCT patients are often unsponsored, and may be unable to afford either of the standard treatments in this study or to attend scheduled study visits. To assure both study adherence and optimal management, treatment and study costs will be covered either by participants' insurance or other funding if the participant does not have insurance, at the discretion of the study site. Reimbursement for travel and time lost for study participation will be at the discretion of each study site. This will help to enable all who need therapy for PCT to be treated within the study.

A history and physical examination will be carried out, which will help document the diagnosis and identify susceptibility factors such as alcohol and estrogen use and smoking, which will then be assessed in more detail by alcohol and smoking questionnaires. The results of the history, physical examination and screening laboratory tests will be recorded on Case Report Forms (CRFs) prepared for this study.

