PCT will be documented by appropriate laboratory measurements carried out in the Porphyria Laboratory at UTMB or another reliable clinical laboratory. This can be done before or after enrollment in an outpatient clinic or at an initial visit to a Clinical Research Center (CRC). Participants are considered to be enrolled after they complete the informed consent process, and will be assigned a Patient Number. Subjects found to be not eligible after enrollment will be recorded as screening failures to be replaced. A recruit to replace approach will be utilized to achieve final recruitment goals. A relapse during follow up can be treated within the study, but will not be part of the primary analysis.

Table 1. Inclusion and exclusion criteria for initial and continued enrollment in the study. Inclusion Criteria:

- 1. Willing to give informed consent
- 2. Willing to return to clinic at time points deemed appropriate by the investigator or work with a local physician to have necessary labs done and samples sent to study site
- 3. Age 18 or greater
- 4. Women of child-bearing potential must be willing to avoid pregnancy and use an accepted and effective contraceptive method during treatment.
- 5. Well-documented PCT:
 - Clinical features- A history of blistering cutaneous photosensitivity and/or skin fragility. Subjects with subclinical PCT who have diagnostic porphyrin elevation but do not have symptoms may also be included.
 - ii.Biochemical and molecular findings a and b are required
 - a. A substantial increase in urinary porphyrins [>450 nmol/24 hours or g of creatinine, or more than 1.5-fold increase (relative to ULN of 300 nmol/24 hours or g of creatinine *or* >300 ug/24 hours or g of creatinine, or more than 1.5-fold increase (relative to ULN of 200 ug/24 hours or g of creatinine)] and/or plasma porphyrins [>2.7 ug/dL, or >3-fold increase (relative to ULN of 0.9 ug/dL), and a fluorescence peak at ~619 nm], with a predominance of uroporphyrin and heptacarboxylateporphyrin in urine or plasma, and normal or only slightly elevated urine ALA and normal PBG.
 - b. Normal or only slightly elevated erythrocyte porphyrins [<200 ug/dL, or less than 1.5-fold increase (relative to ULN of 80 ug/dL)], unless elevated erythrocyte protoporphyrin are due to a non-porphyric condition in the opinion of the investigator. This is to exclude mild cases of CEP and HEP, which may have urine findings similar to PCT.

iii.

Exclusion Criteria:

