- **4.J. Study duration and end of study.** The duration of the study including the Follow Up Phase is at least five years. It is possible that the study will be extended further depending on results and the availability of funding. Subjects will enter the study needing treatment, and require up to 24 months of treatment and observation to document achieving the treatment outcomes, followed by at least 3 years of follow-up. Therefore, the most frequent study visits will occur during the Treatment Phase and generally the first ~12 months of the study, which includes active treatment and the treatment outcome windows to document biochemical remission. Based on the interim analysis (45) it is anticipated that the first outcome (a normal plasma porphyrin concentration) will be reached within 6-7 months, on average. Other treatment outcomes should be achieved within ~12 months, although this is uncertain at present, since such observations were not part of the interim analysis.
- **4.K. Treatment outcomes and schedule of events.** A schedule of events in tabular form and a study flow diagram are shown below. This study compares time to reaching certain efficacy outcomes with the two treatments and documents durability of treatment in terms of absence of increases in porphyrins and recurrence of symptoms.

The primary efficacy outcome is achieving a normal plasma porphyrin concentration (<0.9 mcg/mL). Secondary efficacy outcomes include achieving (1) absence of a fluorescence peak in diluted plasma at neutral pH; (2) a normal level of total urinary porphyrins; (3) a normal pattern of individual porphyrins in urine (defined as total highly carboxylated porphyrins less than coproporphyrin); (4) times to achieving intermediate improvements in these porphyrin

measures, which will be defined during data analysis; (5) absence of new skin lesions for at least 3 months; and (6) effects of susceptibility factors such as hepatitis C, inherited UROD deficiency, etc. on achieving these treatment outcomes.

Durability of treatment (i.e. absence of recurrence) is recorded as beginning with the time that treatment achieves the treatment outcomes, and extends to the time of repeat documentation of a normal plasma porphyrin concentration, assuming there have been no interim recurrences of skin manifestations.

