A total of at least 100 participants will be assigned, based on medical criteria, preference, or (if eligible for both treatments) by randomization, to one of these standard treatment groups. CRFs will be completed for each patient, including porphyrin levels, and data entered into the study database. This database is designed by and housed at the Data Management and Coordinating Center (DMCC) at the University of South Florida in Tampa. The DMCC is supported by the NIH Rare Diseases Clinical Research Network and serves as the secure repository for de-identified data for all consortia in the Network. Upon approval from the UTMB IRB and the Porphyrias Consortium DSMB, data from patients previously enrolled in this study at UTMB starting in 2006 before the study was a RDCRN study will be entered into the database. Subjects will be contacted to give their consent for this data transfer to the DMCC and storage in a federal data repository. For subjects who are now deceased consent will be obtained from next of kin. For subjects who cannot be re-contacted or where the next of kin cannot be re-contacted, approval of the UTMB IRB and the Porphyrias Consortium DSMB will be sought for this data transfer. Transferring this previously collected de-identified data is not expected to cause any increased risks to subjects. Data will be verified and edited where necessary for completeness and consistency by comparison with source documents. Study outcomes, such as time to achieving biochemical endpoints, will be determined from this data. As was found in the interim analysis, assignment to the two groups is unlikely to be equal, and more will be assigned to phlebotomy than to hydroxychloroquine. As in the interim analysis, times to achieving measures of remission are not expected to be substantially different for the two treatment groups. Effects of multiple susceptibility factors and other clinical and demographic features on treatment response and durability will be further examined. Outcome measures such as time to remission will be compared using Cox proportional models to study the effects of susceptibility factors on the hazard ratio to compare the two treatments. All patients who start treatment will be included in the analysis. Safety measures will be compared more descriptively where the adverse effects of each type of treatment are different.

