The following susceptibility factors for PCT will be summarized and tabulated, and examined for balance across treatment groups. Differences in response based on susceptibility factors will be examined by multivariate analysis. The following susceptibility factors will be emphasized in this analysis:

- 1. Alcohol use (presence or absence)
- 2. Smoking (presence or absence)
- 3. Estrogen use (presence or absence)
- 4. Hepatitis C (presence or absence)
- 5. HIV (presence or absence)
- 6. UROD mutations (presence or absence)
- 7. HFE mutations (presence or absence of C282Y and H63D, and specific genotype combinations)

The analysis regarding susceptibility factors will take into consideration that some (e.g. homozygotes for HFE mutations with high ferritin levels) are medical reasons for assignment to one treatment group and not the other. We recognize that because the number of participants in subgroups based on susceptibility factors or combinations of susceptibility factors will be

relatively small, and it may not be possible to detect or exclude statistically significant differences for all susceptibility factors. The data is expected to support continuing this study with larger numbers of participants, or to suggest whether other studies should be designed to clarify the effects of these factors on treatment response and durability.

Additional modeling will assess factors affecting the frequency of recurrence and seasonality effects using logistic regression modeling and log-rank testing, respectively.

Sample Size and Power. A sample size calculation was performed to assess power for a study assessing the effect of factors on time to remission. Extremely common or rare factors are detected with 80% power for 90 subjects (and some dropout) when the hazard ratios are 2.3 (alcohol consumption and UROD deficiency), 2.2 (smoking history), 3.2 (estrogen usage), 2.0 (hepatitis C), and 1.9 (HFE mutations). In summary, this approach for times to remission leads to a sample size of approximately 50 subjects per group. All analyses were conducted in nQuery Advisor Version 5.0 (Janet Elashoff (2002); nQuery Advisor Version 5.0 User's Guide. Los Angeles, CA).

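### The Cox comparison of time to normal plasma porphyrin does not name the baseline value of that same measurement as a covariate or a balance variable

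*Combined protocol and SAP*

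**What the plan says.** The primary outcome is a threshold crossing. Section 4.K states: "The primary efficacy outcome is achieving a normal plasma porphyrin concentration (<0.9 mcg/mL". The introduction to section 4 gives the same limit in a different unit: "After the plasma porphyrin concentration is normal (<0.9 mcg/dL), visits should be scheduled at 4 week intervals". The two units must be reconciled. The working below uses mcg/dL, the unit in which the Background gives starting levels: "Pretreatment plasma porphyrin levels in PCT are generally 10-25 mcg/dL (normal <0.9 mcg/dL".

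On analysis, section 4.R says: "Outcome measures such as time to remission will be compared using Cox proportional models to study the effects of susceptibility factors", with the hazard ratio used to compare the two treatments. It introduces seven factors (alcohol, smoking, estrogen, hepatitis C, HIV, UROD, HFE) with "The following susceptibility factors will be emphasized in this analysis", and plans a check of balance across treatment groups for those factors. The sentence just before the Cox sentence adds that other clinical and demographic features will be examined. It does not name them or say in which model. The Background's conclusions from the interim analysis say: "We consider that age and sex are the clinical features of greatest interest".

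Section 4.B expects most participants to be assigned by medical indication and preference. Baseline plasma and urine porphyrins are in the Schedule of Events. Exclusion criterion 3 in Table 1 also requires pre-treatment values for anyone treated within the past month.

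**The concern.** When the endpoint is the first time a measurement falls below a fixed limit, the starting value bears directly on how long that takes. Two people whose porphyrin clears at the same rate reach the limit at different times if they start at different levels. Where treatment is randomised, starting level should balance on average. Here it is randomised only for the minority eligible for, and willing to have, either treatment.

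A link between assignment and starting level is plausible on the protocol's own account. Table 3 keeps people with high ferritin, continued heavy drinking or marked liver abnormality off hydroxychloroquine. The Background says iron is essential to the enzyme inhibition that makes porphyrins accumulate. If phlebotomy patients start higher for such reasons, an unadjusted Cox model would read the difference as slower remission with phlebotomy.

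The protocol expects the study to shape treatment guidelines. It is also unblinded and its interim results are published. Both are reasons to fix the covariates in advance.

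**Working it through.** **The plan's own figures.** The hazard ratios in 4.R (1.9 to 3.2 at 80% power with 90 subjects) are for susceptibility factors. No power or target is stated for the treatment comparison, so there is no figure to reproduce here and none that this point changes.

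**Inputs from the documents.** Limit 0.9 mcg/dL; usual starting levels 10-25 mcg/dL (Background); time to the primary endpoint between 6 and 7 months in both arms, taken as 6.5 (interim results); 100 participants (4.R); a 17:13 split among evaluable interim patients, about 57:43.

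**Assumed inputs.** Log-linear decline, the spread of individual rates, the size of any imbalance, and the lag in step 2. The documents give none of these.

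**Step 1: no lag.** With baseline B and rate k, t = ln(B/0.9)/k.
- B = 10: ln(11.11) = 2.408
- B = 25: ln(27.78) = 3.324
- Ratio: 3.324/2.408 = 1.38, so 38% longer.

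Set 6.5 months at the geometric mean, √(10 × 25) = 15.8, where ln(15.8/0.9) = 2.866:
- B = 10: 6.5 × 2.408/2.866 = 5.5 months
- B = 25: 6.5 × 3.324/2.866 = 7.5 months

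**Step 2: assumed lag of 3.5 months before the fall starts.** That leaves 3.0 months of decline at the geometric mean.
- B = 10: 3.5 + 3.0 × 2.408/2.866 = 6.0 months
- B = 25: 3.5 + 3.0 × 3.324/2.866 = 7.0 months
- Ratio: 6.98/6.02 = 1.16, so 16% longer.

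**Step 3: imbalance with no true treatment difference.** Simulated Cox models, 100 participants split 57:43, one arm starting 30% higher, 10-25 taken as ±1 SD on the log scale, SD of log rate 0.2-0.5. The hazard ratio is for the arm that starts higher.

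| Model | Unadjusted HR | False positives |
|---|---|---|
| No lag, first set of runs | 0.72-0.85 | 10-29% |
| No lag, second set of runs | 0.72-0.85 | 14-37% |
| Median 3.5-month lag, both arms | 0.84-0.90 | 9-13% |

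In the first set, adding log baseline returned the HR to 1.00-1.02, with rejection about 6%.

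**Step 4: balanced arms with a true effect.** Power without and with log baseline:
- 95% of starts within 10-25: 63% against 68% (SD of log rate 0.25), and 69% against 71% (SD 0.5).
- 10-25 as ±1 SD: 47-93% against 51-99% across settings, a gain of 4-6 points.

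In the first of these settings, omitting baseline also pulled the HR slightly toward 1 (1.62 against 1.69, and 1.68 against 1.70). That matters a little for a study whose hypothesis is that the treatments are comparable.

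**The case against.** **The plan does not exclude baseline porphyrin.** This stands. The seven factors are those to be emphasised, not a closed list, and 4.R mentions further features. A reader might infer that the plan rules out baseline porphyrin, age and sex; the documents support only that none is specified as a covariate. An unnamed set of features still fixes nothing in advance.

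**No imbalance is shown.** This also stands. Porphyrin level is not an assignment criterion in Tables 3 or 4, and no baseline level is reported by arm. The reported similarity of randomised and non-randomised participants does not settle the matter, because it does not compare the treatment arms.

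**A single decay rate does not match either arm.** The protocol says levels may first rise on hydroxychloroquine. For phlebotomy it gives 3-4 months to target ferritin and 6-7 months to remission, with porphyrin reaching normal usually within several weeks of stopping. The 38% is therefore an upper illustration. The lagged model gives a smaller effect in the same direction.

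**Other determinants are better documented.** The text names initial ferritin and adherence as influences on the course of treatment, and ferritin also drives assignment. Nothing in the documents supports calling baseline porphyrin the strongest predictor. Adjusting for it does not remove confounding by ferritin.

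**Two further inferences fail.** One might read "plasma porphyrins [>2.7 ug/dL, or >3-fold increase (relative to ULN of 0.9 ug/dL" as a lower bound on plasma level at entry, but Table 1 accepts raised urinary porphyrins and/or raised plasma porphyrins, so entry on urine alone is possible. And because section 4.D says "we expect to enroll 8-10 patients with new onset or recurrent PCT per year at UTMB", one might say that the recurrence model's factor list omits new versus recurrent disease. Section 4.R gives no factor list for recurrence, so there is no list to fault.

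**The analysis is called descriptive.** It is, but 4.R still specifies a hazard ratio to compare the treatments.

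**Conclusion.** The gap is real and worth closing, with medium confidence. The measurement that defines the endpoint has a recorded baseline value that is named neither in the Cox model nor in the balance check, in a comparison that is mostly not randomised.

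The case rests on confounding, and it is conditional: bias requires a difference in starting level between arms. It would go too far to conclude that the treatment hazard ratio will be biased. Given an assumed 30% difference, the unadjusted HR moves to about 0.72-0.90, with false positives of roughly 9-37%. Both ranges depend on the assumed decline, lag and rate variation. Power is a minor argument, at about 2-6 points when starting levels are near the usual range.

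**What to change.** In 4.R:

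1. Pre-specify log baseline plasma porphyrin as a covariate in the Cox treatment comparison of time to normal plasma porphyrin. Use the matching baseline urine value for the total urine porphyrin outcome.
2. Name age and sex as covariates, in line with the Background.
3. Add baseline porphyrin, by arm, to the balance table.
4. Report susceptibility-factor effects with and without baseline porphyrin. A factor may act partly by raising the starting level, in which case adjustment would remove part of its effect.

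The cost is wording, since baseline porphyrins are already collected, plus about three degrees of freedom. That is not free: the model already carries treatment, seven factors and HFE genotype combinations. If the interim proportion with an evaluable primary outcome (30 of 48) held for 100 participants, an assumption, there would be about 100 × 30/48 ≈ 62 events. If events are that few, 4.R should say which covariates belong to the primary treatment comparison and which to the exploratory factor models.
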